7.2 Statistical Analyses

Data analysis from this multi-center clinical trial will be performed to characterize 2D and 4D CEUS as a follow-up imaging tool for the evaluation of residual tumoral blood flow in patients with HCC treated with TACE.

Our statistical analysis will address three major questions:

1. Does 2D and 4D CEUS 1-2 weeks post TACE yield sensitivity and specificity greater than 90% for identifying residual tumor blood flow, thereby providing reliable earlier identification (relative to the current clinical standard) of patients in need of retreatment?
2. Does 2D and 4D CEUS 1 month post TACE yield sensitivity and specificity greater than 90% for identifying residual tumor blood flow, thereby providing an accurate, safe, and cost-effective imaging alternative for identifying TACE patients in need of retreatment?
3. Are quantifiable biomarkers generated by parametric imaging of 2D and 4D CEUS exams able to differentiate between fully treated and incompletely treated masses by measuring blood flow kinetics?

The first three cases at each institution will be used as reader training cases and will not be included in the final analysis. In the event of all cases showing identical response (i.e. all incompletely or completely treated), the first case with an alternative outcome will be substituted for the 9th case. Following reader training, each reader (all of whom have previous experience with CEUS and volumetric ultrasound) will be asked to evaluate all 201 remaining cases. 2D and 4D CEUS exams will be read separately and only after randomization. 2D cases will be viewed in a standard DICOM viewer, while 4D cases will be viewed in GE's 4D View software. Readers will first be asked to review both the patient's baseline CE-MRI/CT and CEUS exams to identify the size and location of the treated mass. Following baseline review, each reader will review the 1-2 week and 1 month CEUS exam (in random order). Intratumoral blood flow will be assessed as present or not present. Readers will then be asked to interpret the patient's 1 month follow-up CE-MRI/CT images and again evaluate the need to retreat based on residual blood flow. Finally, when available, readers will review subsequent CE-MRI/CT imaging studies (up to six months post TACE). MRI/CT evaluations will be based on mRECIST criteria. All imaging studies will be read twice by each

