reader. Studies will be presented in random order. The second round reads will be performed at least one month after the first. Outcomes will be defined as incompletely treated (i.e. requiring retreatment) based on (in order of preference of reference standard): a) pathological examination of explanted livers demonstrating live tumors; b) tumor enhancement seen with CT or MR and confirmed via angiography during retreatment; c) tumor growth on 6 month follow-up CE-CT/MRI; or d) asymmetrical or nodular tumor enhancement on CE-MRI/CT on 6 month follow-up. Incomplete treatment on CEUS (2D or 4D) will be evaluated by each reader and evidenced by the tumor showing either residual blood flow after treatment or nodular peripheral blood flow.

For questions 1-2, sensitivity (the ability to detect patients in need of retreatment) and specificity (the ability to identify patients who do not require retreatment) will first be calculated on a reader by reader basis. Four 2 x 2 tables will be constructed comparing the need for re-treatment based on the clinical gold standard described above and CEUS, tabulating true positives, false positives, false negatives, and true negatives. A table will be created for CEUS at 1-2 weeks and 1 month for both 2D and 4D CEUS and used to calculate sensitivity, specificity, accuracy, positive predictive value, and negative predictive value. Statistical significance between the reference standard and each of the 4 CEUS groups will be determined using a McNemar test. These values will also be calculated based on the majority decision (i.e. 4 or more readers in agreement). In the event of discordant readings during this analysis, tumor outcome will be decided by consensus by the two readers at TJU. Differences between techniques (2D vs. 4D) and time points (1-2 weeks vs. 1 month post treatment) will be determined by comparing areas under the receiver operating characteristic curves for each modality/time point based on necessity of tumor retreatment. Intra-rater and inter-rater variability will be calculated using a Shrout and Fleiss Interclass Correlation [Shrout and Fleiss 1979]. Finally, a logistical regression and analysis of variance will be performed to determine if significant variations exist between individual sites (to determine operator dependence), lesion size (tumor size dependency) or between patients treated with cTACE vs. DEB-TACE (treatment dependency).

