For statistical question 3, all quantitative parameters will be compared between fully treated and incompletely treated masses using a Student's t-test. Additionally, lesions that demonstrate lack of residual enhancement at 1 month, but show recurrence at 6 month follow-up, will be compared to completely treated masses to determine if quantitative CEUS parameters can detect this lower level of residual disease. Statistical analysis will be performed with assistance from the biostatistician co-investigator using Stata 12.0 (Stata Corp, College Station, TX) with p values < 0.05 considered statistically significant after a Bonferroni-type adjustment for multiple tests. These statistical tests will answer our three major questions regarding the sensitivity and specificity of 2D and 4D CEUS as an imaging tool for the follow-up of TACE

at 1-2 weeks and 1 month (specific aims 1-2), as well as the influence of operator, reader, tumor size, and embolization material.

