7.2.1 Sample Size Justification

As the most clinically important aims, aims 1-2 will be used as the basis for the sample size analysis, where each patient represents an independent data point used to evaluate the technique's sensitivity and specificity at both 1-2 weeks and 1 month follow-up times. Based on our pilot studies using 2D CEUS to evaluate TACE performed using Lipiodol [Kono et al. 2007] or drug-eluting-beads [Shaw et al. 2014], we expect to encounter a patient population in which up to 67% of patients require retreatment. A sample size analysis was performed using a binomial test with One-Sample Sensitivity and Specificity Analysis in NCSS/PASS 2008 (NCSS, East Kaysville, UT) to estimate the number of cases required to produce a over 85% power for this study. This analysis assumes sensitivity and specificities of 98%, an alpha of 0.05, prevalence of disease of 66.7%, and null sensitivity and specificities of 90%. Results from this analysis are provided in tabular format below.

Preva- ---- Power ----		Sample	--- Sensitivity ---		--- Specificity ---		----- Alpha -----			P
Size	H0 Sens. Spec.	H1 N1 and N	H0 Se0	H1 Se1	Sp0	Sens. Sp1	Spec. Target	lence Actual	Actual	P
0.0000	0.0000	7								
10	0.9000	0.9800	0.9000	0.9800	0.0500	0.0000	0.0000	0.6670		
0.0000	0.0000	13								
20	0.9000	0.9800	0.9000	0.9800	0.0500	0.0000	0.0000	0.6670		
0.0000	0.0000	20								
30	0.9000	0.9800	0.9000	0.9800	0.0500	0.0000	0.0000	0.6670		
0.0000	0.0000	27								
40	0.9000	0.9800	0.9000	0.9800	0.0500	0.0000	0.0000	0.6670		
0.5134	0.0000	33								
50	0.9000	0.9800	0.9000	0.9800	0.0500	0.0309	0.0000	0.6670		
0.4457	0.0000	40								
60	0.9000	0.9800	0.9000	0.9800	0.0500	0.0148	0.0000	0.6670		
0.7581	0.0000	47								
70	0.9000	0.9800	0.9000	0.9800	0.0500	0.0440	0.0000	0.6670		
0.7135	0.0000	53								
80	0.9000	0.9800	0.9000	0.9800	0.0500	0.0259	0.0000	0.6670		
0.6619	0.5455	60								
90	0.9000	0.9800	0.9000	0.9800	0.0500	0.0138	0.0424	0.6670		
0.8494	0.5134	67								
100	0.9000	0.9800	0.9000	0.9800	0.0500	0.0307	0.0309	0.6670		
0.8202	0.4735	73								
110	0.9000	0.9800	0.9000	0.9800	0.0500	0.0190	0.0203	0.6670		
0.9231	0.4457	80								
120	0.9000	0.9800	0.9000	0.9800	0.0500	0.0353	0.0148	0.6670		
0.9027	0.4195	87								
130	0.9000	0.9800	0.9000	0.9800	0.0500	0.0211	0.0108	0.6670		
0.9608	0.7581	93								
140	0.9000	0.9800	0.9000	0.9800	0.0500	0.0382	0.0440	0.6670		

0.9492	0.7358	100							
150	0.9000	0.9800	0.9000	0.9800	0.0500	0.0237	0.0338	0.6670	

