0.9791	0.7135	107							
160	0.9000	0.9800	0.9000	0.9800	0.0500	0.0374	0.0259	0.6670	
0.9735	0.6839	113							
170	0.9000	0.9800	0.9000	0.9800	0.0500	0.0255	0.0181	0.6670	
0.9893	0.6619	120							
180	0.9000	0.9800	0.9000	0.9800	0.0500	0.0382	0.0138	0.6670	
0.9857	0.8879	127							
190	0.9000	0.9800	0.9000	0.9800	0.0500	0.0250	0.0421	0.6670	
0.9945	0.8494	133							
200	0.9000	0.9800	0.9000	0.9800	0.0500	0.0385	0.0307	0.6670	

A total of 201 patients will be used in the final analysis for this study (the first 9 will be used as training cases and excluded), of which 135 (66.7%) will require retreatment. A total sample size of 201 (which includes 133 subjects with the disease) achieves 99% power to reject the null hypothesis for sensitivity, and 85% power to reject the null hypothesis for specificity.

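### The 85% specificity power ignores the plan's own Bonferroni-type adjustment; split over four tests, power is about 61% with 67 negatives (55% averaged over a random number of negatives)

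*Combined protocol and SAP*

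**What the plan says.** Section 7.2 poses two primary questions, one for each time point. The first reads "Does 2D and 4D CEUS 1-2 weeks post TACE yield sensitivity and specificity greater than 90" per cent, and the second asks the same at 1 month. Two modalities at two times make four CEUS groups, each with a sensitivity and a specificity claim.

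On testing, section 7.2 says: "Statistical significance between the reference standard and each of the 4 CEUS groups will be determined using a McNemar test". It sets the threshold as "p values < 0.05 considered statistically significant after a Bonferroni-type adjustment for multiple tests". The number and identity of the tests adjusted for are not given. The next sentence says: "These statistical tests will answer our three major questions regarding the sensitivity and specificity of 2D and 4D CEUS", and goes on to name specific aims 1-2. The Synopsis carries the same adjustment rule.

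Section 7.2.1 bases the sample size on aims 1-2 and uses a one-sample binomial test "to estimate the number of cases required to produce a over 85% power for this study". On inputs it says: "This analysis assumes sensitivity and specificities of 98%, an alpha of 0.05, prevalence of disease of 66.7" per cent, with null values of 90%. It does not state sidedness and does not mention the adjustment. It concludes that 201 patients "achieves 99% power to reject the null hypothesis for sensitivity, and 85% power to reject the null hypothesis for specificity".

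**The concern.** The sample size section spends the whole 0.05 on a single test. The analysis section says no result counts until the threshold has been adjusted for multiple tests. Nothing reconciles the two. More than one primary test is certain, because four CEUS groups are each to be judged against 90%.

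Specificity is where this matters. It rests on about a third of the patients, and its stated power has no margin over the target. Any tightening of alpha therefore takes the design below the power it was sized for. Because the family is undefined, whether a borderline specificity result counts as a success could also be settled after the data are seen.

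**Working it through.** **Inputs (section 7.2.1).** Null 0.90, alternative 0.98, alpha 0.05, prevalence 66.7%, analysed N = 201. The N = 200 table row has 133 positives, hence 67 negatives.

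**Method.** Exact binomial test. The critical count r is the smallest with P(X ≥ r | n, 0.90) ≤ alpha; power is P(X ≥ r | n, 0.98).

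**Reproducing the plan's figures, one-sided 0.05.**
- Sensitivity, n = 133: r = 126, actual alpha 0.0385, power 0.9945.
- Specificity, n = 67: r = 65, actual alpha 0.0307, power 0.8494.

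Both match the N = 200 row. A two-sided 0.05 test would give 61.2% for specificity, so the stated 85% is one-sided. (The N = 190 specificity entry, 0.8879, does not reproduce; I get 0.8679. It has no bearing here.)

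**Specificity at 67 negatives, term by term.**

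| Correct | Probability if true value is 0.90 | Probability if true value is 0.98 |
|---|---|---|
| 67 | 0.90^67 = 0.00086 | 0.98^67 = 0.2583 |
| 66 | 67 × 0.10 × 0.90^66 = 0.00640 | 67 × 0.02 × 0.98^66 = 0.3532 |
| 65 | 2211 × 0.10² × 0.90^65 = 0.02346 | 2211 × 0.02² × 0.98^65 = 0.2379 |

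Here 2211 = 67 × 66 / 2. Cumulating from the top:
- P(X ≥ 66 | 0.90) = 0.00726 and P(X ≥ 65 | 0.90) = 0.0307.
- Two tests allow 0.025 each and six allow 0.05/6 = 0.0083. Both lie between 0.00726 and 0.0307, so every family of two to six tests requires 66/67.
- Power is then 0.2583 + 0.3532 = 0.6115, against 0.8494 unadjusted.
- The difference, 0.2379, is the chance of exactly 65/67, where the conclusion depends on the adjustment.

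With four tests and 66 or 68 negatives (section 7.2.1 gives both 135 and 133 diseased among 201), power is 61.9% or 60.5%.

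**Random number of negatives.** The number of negatives will not be fixed, so I weighted the power at each n by Binomial(201, 0.333).

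| Tests in family | Alpha each | Specificity, n = 67 | Specificity, averaged | Sensitivity, n = 133 |
|---|---|---|---|---|
| 1 | 0.05 | 84.9% | 82.7% | 99.5% |
| 2 | 0.025 | 61.2% | 69.4% | 98.2% |
| 4 | 0.0125 | 61.2% | 54.8% | 94.8% |
| 8 | 0.00625 | 25.8% | 39.8% | 87.1% |

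**Joint power for one group.** Positives and negatives are different patients, so the two powers multiply.
- Unadjusted: 0.9945 × 0.8494 = 84.5% (82.1% averaged).
- Four tests: 0.9483 × 0.6115 = 58.0% (52.2% averaged).

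**Prevalence.** The plan expects "up to 67% of patients require retreatment", and section 1.1 gives 65-75% for tumours, also as an upper bound. Averaged specificity power:

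| Prevalence | Unadjusted | Four tests |
|---|---|---|
| 60% (assumed) | 90.2% | 68.7% |
| 65% | 84.8% | 58.5% |
| 66.7% | 82.7% | 54.8% |
| 70% | 77.1% | 44.8% |
| 75% | 66.4% | 34.4% |

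**The case against.** The adjustment sentence sits in the paragraph on question 3, straight after t-tests of many quantitative parameters. The test against 90% is not among the tests listed in section 7.2; it appears only in 7.2.1. The sponsor may have meant questions 1-2 to be unadjusted, in which case 85% stands for each single test. That intention is possible, but the text does not express it: the sentence that follows extends the tests to all three questions and to aims 1-2 by name.

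The family of four is also open to challenge. The questions join 2D and 4D in the same way as they join sensitivity and specificity, so one could count two tests, one per time point. The averaged loss is then smaller (82.7% to 69.4%). With 67 negatives it is unchanged, since two to six tests all need 66/67.

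Two further points stand as qualifications. Like must be compared with like: 84.9% with 61.2% at fixed n, or 82.7% with 54.8% averaged. About two points of the gap between 85% and 55% come from the random number of negatives, not from multiplicity. And 0.8494 is already marginally short of a target above 85%, before any adjustment. The one-in-four chance of a result that turns on the rule applies to exactly 67 negatives and a true specificity of 98%; averaged, the gap between no adjustment and two tests is 13.3 points (82.7 − 69.4).

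**Conclusion.** The concern holds. The stated powers are arithmetically right for a single one-sided test at 0.05, but that is not the rule section 7.2 sets for declaring significance. Under an adjustment over two to six tests, specificity power with 67 negatives is 61.2%. Averaged over the number of negatives, it is 69.4% for two tests and 54.8% for four. Sensitivity power stays near 95% with four tests, so the weakness lies in specificity and hence in the joint claim (58.0%, or 52.2% averaged).

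This rests on the plan's 90% and 98% values, one-sided exact tests, and the adjustment applying to questions 1-2. The four-test family is an assumption: it follows if sensitivity and specificity must both pass within a group, so that alpha need not be split between them. A lower prevalence would help, but at an assumed 60% the averaged four-test figure is still only 68.7%. The arithmetic and the gap in the plan are certain; the family size is for the sponsor to state. This should be fixed before any reads are analysed.

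**What to change.** In section 7.2, state that:
- each comparison with 90% is a one-sided exact binomial test;
- the majority read is primary, giving one result per patient;
- sensitivity and specificity within a CEUS group are co-primary, so both must pass and alpha is not split between them;
- the family consists of named tests.

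Then choose one of two rules.

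(a) Keep Bonferroni over the four groups, at 0.0125 each. Restate in 7.2.1: specificity power about 61% with 67 negatives (55% averaged), sensitivity about 95%, joint 58% (52% averaged). The price is a much lower stated power.

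(b) For these tests, replace Bonferroni with a pre-stated order of the four groups, each at 0.05, stopping at the first failure. Restate joint power as about 84% (82% averaged) for the first group only. The price is that a later group can be claimed only if all earlier ones pass, so the order must be fixed before any reads are analysed.

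If questions 1-2 were meant to be unadjusted, section 7.2 must say so and 7.2.1 should describe 85% as a per-test figure. Each of these changes is to wording only and needs no extra patients.

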APPENDIX A - INVESTIGATOR OBLIGATIONS

A. Institutional Review Board (IRB) and Human Subjects Research Review Board (HSRRB) Review/Approval

The protocol and informed consent for this study must be reviewed and approved by an appropriate IRB and HSRRB prior to enrollment of participants in the study. It is the responsibility of the investigator to assure that all aspects of the ethical review are conducted in accordance with FDA Regulations 21 CFR Part 56. A letter documenting the IRB and HSRRB approval which specifically identifies the study/protocol must be obtained by the investigator prior to initiation of the study. Amendments to the protocol will be subject to the same requirements as the original protocol. The HSRRB must review and approve each modification to the study prior to implementation.

A progress report with a request for re-evaluation and re-approval will be submitted by the investigator to the IRB and HSRRB at intervals required by the IRB, and not less than annually.

After completion or termination of the study, the investigator will submit a final report to the IRB. This report should include: deviations from the protocol, the number and types of participants evaluated, the number of participants who discontinued (with reasons), results of the study, if known, and all AEs, including deaths.

B. Informed Consent

Signed, written informed consent which conforms to FDA Regulation 21 CFR Part 50, must be obtained from each participant prior to entering the study. Each participant will be provided a written consent form and verbal information in an understandable manner which describes the nature and duration of the study. The research study coordinator or the investigator will conduct the informed consent interview in a private examination room. The potential subject will be allowed to discuss the study with the investigator, research study coordinator, or any persons who may have accompanied the potential subject. Additionally, the participant must be allowed adequate time to consider the potential risks and benefits associated with his participation in the study. The research study coordinator will sign the informed consent as the person conducting the consent interview.

C. Data Reporting and Data Forms

Data reflecting participant's experiences with the study will be recorded on CRFs by the investigator.

D. Records Retention

All records pertaining to the conduct of the clinical study, including CRFs, informed consent forms, source documents, and other study documentation must be retained for seven (7) years after the end of the study.

Other study documentation includes all protocols and amendments, drug supply receipt, dispensing and final disposition records, IRB correspondence and approvals, signed consent forms, a blank copy of study consent forms, Form 1572, curriculum vitae or biosketches of members of the research team including the medical monitor, HSRRB correspondence and approval, and Statement of Investigator forms.

Source documents include all original records of observations, results, and activities necessary to

reconstruct and evaluate the study. Source documents include but are not limited to laboratory reports, electrocardiogram tracings, X-ray films, ultrasound images, subject diaries, subject progress notes, hospital charts, appointment books, radiologic reports or pharmacy records, and any other records or reports of procedures performed during the study. Source documents also may include copies of the CRF or sponsor supplied worksheets when original information is recorded directly onto these forms.

Whenever possible, an original recording of an observation should be retained as the source document. However, a photocopy of a record is acceptable provided it is legible and is a verified copy of the original document.

E. Deviation from the Protocol

The investigator will not deviate from the protocol without prior written approval from the IRB and the HSRRB. In medical emergencies, the investigator will use medical judgment and remove the participant from immediate hazard. The HSRRB and the IRB will be notified regarding the type of emergency and course of action taken. Any other changes to or deviations from the protocol will be made as an amendment to the protocol. The amendment must be submitted for review and approval to the local IRB and the HSRRB for review and approval.

F. Roles and Responsibilities of Study Personnel

[name]., Assistant Professor of Radiology, TJU will serve as Principal Investigator on this project. He will be responsible for the scientific goals of the project. [name] will oversee patient recruitment, informed consent, ultrasound studies, and the data entry and statistical analyses. He will also supervise the data acquisition from patients.

APPENDIX B – DEFINITY PRODUCT INSERT

Appendix C

UNANTICIPATED PROBLEM REPORT FORM

For Sub-Site Reporting

Thomas Jefferson University Principal Investigator: _____

Sub-Site Principal Investigator: _____

TJU IRB Control Number/Sub-Site Identifier: _____

Protocol Title: _____

Subject ID: _____ Approx. Date of Problem: _____ Date Aware: _____

Description of Problem: _____

Is this Unanticipated Problem a Protocol Deviation? Yes No

Did the Unanticipated Problem pose risk to subjects or others? Yes No

If no, have PI or Co-I sign the form. If YES, describe the risk below:

Describe the Corrective Action Plan: _____

Has the problem been resolved? Yes No

Does the consent or protocol require modification? Yes No

Signature of person preparing report Date Email/Phone number

Sub-site PI signature Date Email/Phone number
